### 10.9.1 Adverse events

All adverse events recorded during the treatment period and up to 30 days after the last study dose intake will be summarized by treatment group with descriptive statistics for the Safety population.

All adverse events will be assigned to a Preferred Term (PT) and will be classified by primary System Organ Class (SOC) according to the MedDRA thesaurus version 20.1. Adverse events will be reported on a per-patient basis. This means that even if a patient reports the same event repeatedly (i.e. events mapped to the preferred term) the event will be counted only once. In the latter case, the event will be assigned the worst intensity and the strongest relationship to the study drug.

For summaries, the drug-event relationship will be shown as “*Related*” if relationship with study treatment is assessed as “*Certain*”, “*Probable*” or “*Possible*” by the Investigator; otherwise the event is considered as “*Unrelated*”. Missing categories will be considered as related.

Treatment emergent events, defined as those AEs that start or worsen after the start of apixaban/dalteparin and up to 30 days after the last study dose intake, will be summarized by treatment group, System Organ Class, and Preferred Term, and also by event severity and by the event’s relationship to study treatment.

The following listing and tables will be presented:

- 1) An overview of adverse events with the number of patients who exhibited at least one AE, number of adverse events, number of patients who exhibited at least one TEAE, number of TEAEs, number of patients who reported at least one related TEAE, number of related TEAEs, number of patients who reported at least one treatment-emergent serious adverse event (TESAE), number of TESAEs, number of patients who reported at least one related TESAE, number of related TESAEs, number of patients who reported at least one AESI, number of AESI, number of patients who died, number of patients who temporarily discontinued the study drug due to an adverse event, number of patients with premature

withdrawal due to an adverse event;

- 2) An overview of adverse events with the number of patients who exhibited at least one TEAE with DVT as study outcome, number of TEAEs with DVT as study outcome, number of patients who exhibited at least one TEAE with PE as study outcome, number of TEAEs with PE as study outcome, number of patients who reported at least one TEAE with bleeding as study outcome, number of TEAEs with bleeding as study outcome, number of patients who reported at least one TEAE with major bleeding as study outcome, number of TEAEs with major bleeding as study outcome, number of patients who reported at least one TEAE with clinically relevant non-major bleeding as study outcome, number of TEAEs with clinically relevant non-major bleeding as study outcome, number of patients who reported at least one TEAE with clinically relevant bleeding as study outcome, number of TEAEs with clinically relevant bleeding as study outcome, number of patients who reported at least one TEAE with myocardial infarction as study outcome, number of TEAEs with myocardial infarction as study outcome, number of patients who reported at least one TEAE with ischemic stroke as study outcome, number of TEAEs with ischemic stroke as study outcome, number of patients who reported at least one TEAE with other venous thrombotic events as study outcome, number of TEAEs with other venous thrombotic events as study outcome, number of patients who reported at least one TEAE with other arterial thrombotic events as study outcome, number of TEAEs with other arterial thrombotic events as study outcome.
- 3) Summary of all TEAEs by treatment group, primary System Organ Class and Preferred Term;
- 4) Summary of all TEAEs by treatment group, primary System Organ Class, Preferred Term and Intensity;
- 5) Summary of all TESAEs by treatment group, primary System Organ Class and Preferred Term;
- 6) Summary of all non-serious TEAEs by treatment group, primary System Organ Class and Preferred Term (where PT occurred at a frequency of  $\geq 5\%$ );
- 7) Summary of all Related TEAEs by treatment group, primary System Organ Class and Preferred Term;
- 8) Summary of all Related TESAEs by treatment group, primary System Organ Class and Preferred Term;
- 9) Summary of all AESI by treatment group, primary System Organ Class and Preferred Term;
- 10) Patient Listing of Deaths;
- 11) List of TEAEs by patient;
- 12) List of TESAEs by patient;
- 13) List of Related TEAEs by patient;
- 14) List of Related TESAEs by patient;
- 15) List of AESI by patient;
- 16) List of Patients with Adverse Events Leading to Withdrawal from study drug;
- 17) List of Patients with Adverse Events Leading to temporary discontinuation of study drug.

The number and the percentage of patients with at least one TEAEs by SOC and Preferred Term, and the number of events will be presented for the statistical summary from the above points #3 to

#9.

Adverse events with start date before the first study dose intake or after 30 days the last study dose intake will be only listed.

#### **10.9.1.1 Safety study outcomes**

Possible safety study outcomes are: DVT, PE, bleeding, acute myocardial infarction, ischemic stroke, other venous thrombotic events, other arterial thrombotic events.

A frequency table on safety study outcomes will be produced. Details of each category of the study outcomes will be summarized by treatment group with default statistics: number and percentage of patients with the study outcomes and the number of events reported will be presented.

Default frequency tabulations (n,%) will be provided for the following categorical variables characterizing the safety study outcomes:

##### **DVT**

- Specific type of DVT (Symptomatic / Unsuspected);
- Location of DVT (Upper limbs, Vena Cava, Vena iliaca right / Vena iliaca left / Vena iliaca bilateral, Right femoral vein / Left femoral vein / Bilateral femoral vein, Right popliteal vein / Left Popliteal vein / Bilateral Popliteal vein, Right Distal vein / Left Distal vein / Bilateral Distal vein, Other);
- If symptomatic, type of symptoms (Pain, Redness, Calf pain of tenderness, Swelling of extremities, Tenderness along deep vein, Additional relevant DVT findings);
- Confirmatory tests (Compression ultrasonography, Venography, CT Venography, MR Venography, Other);
- Event resulting in discontinuation or interruption of patient's cancer treatment (Yes / No).

##### **PE**

- Specific type of PE (Symptomatic / Unsuspected);
- Location of DVT (Right pulmonary artery / Left pulmonary artery / Bilateral pulmonary artery, Trunk, Right lobar branch / left lobar branch / Bilateral lobar branch, Segmentary-subsegmentary artery, Other);
- If symptomatic, type of symptoms (Breathing difficulties including dyspnea and tachypnea, Chest pain, Hemoptysis, Tachycardia, Fever, Cyanosis, Other);
- Confirmatory tests (CT pulmonary angiography, pulmonary angiogram, VQ scan, perfusion scan, echocardiogram, other);
- Event resulting in discontinuation or interruption of patient's cancer treatment (Yes / No).

##### **Bleeding**

- Single episode / Repetitive bleeding. If repetitive bleeding and main duration of each episode known: duration (hours)
- Major bleeding (Yes / No).

If major:

- Decrease in hemoglobin of 2 g/dl (1.2 mmol/L) or more (Yes / No);
- Transfusion of 2 or more units of packed red blood cells (Yes / No);

## STATISTICAL ANALYSIS PLAN

Version: 1.3

Date: 29OCT2019

Sponsor: Fondazione FADOI

Study Protocol: CARAVAGGIO (FADOI 03.2016)

- Bleeding that occurs in at least one critical site (Yes / No);
  - Intracranial (Yes / No);
  - Intra-spinal (Yes / No);
  - Intra-ocular (Yes / No);
  - Pericardial (Yes / No);
  - Intra-articular (Yes / No);
  - Intramuscular with compartment syndrome (Yes / No);
  - Retroperitoneal (Yes / No).
- Fatal bleeding (Yes / No);
- Surgical intervention needed (Yes / No).

- Clinically relevant non-major bleeding (Yes / No).

If yes:

- Bleeding compromising hemodynamics (Yes / No);
- Spontaneous hematoma larger than 25 cm^2 (no traumatic cause) (Yes / No);
- Spontaneous hematomas larger than 100 cm^2 (traumatic cause) (Yes / No);
- Intramuscular hematoma documented by Ultrasonography (Yes / No);
- Epistaxis requiring tamponade or other medical intervention (Yes / No);
- Gingival bleeding (Yes / No);
- Bleeding from venipuncture for > 5 minutes (Yes / No);
- Spontaneous macroscopic hamtura (Yes / No);
- Macroscopic hematuria which lasted for more than 24 hours after invasive procedures (Yes / No);
- Hemoptysis requiring endoscopy or other medical intervention (Yes / No);
- Hematemesis requiring endoscopy or other medical intervention (Yes / No);
- Spontaneous rectal bleeding requiring endoscopy or other medical intervention (Yes / No).

### Ischemic stroke

- Duration of symptoms (less than 24 hours / more than 24 hours);
- Assessment by imaging or autopsy (Yes / No). If yes, Non-hemorrhagic / Infarction with hemorrhagic conversion);
- Therapeutic intervention (Yes / No).

### Myocardial infarction

- CK-MB  $\geq$  2 x ULN (Yes / No / Not available);
- Troponin T  $\geq$  2 x ULN (Yes / No / Not available);
- Troponin I  $\geq$  2 x ULN (Yes / No / Not available);
- Total CK  $\geq$  2 x ULN (Yes / No / Not available);
- ECG performed (Yes / No). If yes, new significant Q-waves  $\geq$  0.04 seconds in  $\geq$  2 contiguous leads? (Yes / No).

Other venous thrombotic events

- Clinical sign (Yes / No);
- Location (splanchnic vein thrombosis, cerebral vein thrombosis, genitourinary vein thrombosis, other)

Other arterial thrombotic events

- Clinical sign (Yes / No);
- Location (carotid artery thrombosis, femoral artery thrombosis, iliac artery thrombosis, renal artery thrombosis, retinal artery thrombosis, other).

Analysis will be performed on the Safety analysis set.

**10.9.2 Laboratory evaluation**

Clinical laboratory data will be summarized for each treatment group at each measurement time point and for each patient's final post-baseline measurement in the following ways:

- (1) with descriptive statistics (mean, standard deviation, median, and range) for each measurement time point;
- (2) with descriptive statistics for the change from baseline in the measurements at each post-baseline time point;
- (3) with shift tables summarizing the frequencies of patients below, within, and above the normal ranges at each time point as compared with baseline.

All clinical laboratory values collected during the study will be listed, with values outside the normal ranges flagged for clinical evaluation.

Presentations will use SI Units.

To convert from the conventional unit to the SI unit, multiply by the conversion factor:

Parameter	Conventional Unit	Conversion Factor	SI Unit
Hematocrit	%	0.01	Proportion of 1.0
Hemoglobin	g/dL	10	g/L
RBC count	$\times 10^6/\mu\text{L}$	0.1	$\times 10^{12}/\text{L}$
WBC count	$\times 10^3/\mu\text{L}$	1	$\times 10^9/\text{L}$
Platelets count	$\times 10^3/\mu\text{L}$	1	$\times 10^9/\text{L}$
Creatinine	mg/dL	76.25	$\mu\text{mol}/\text{L}$
Total Bilirubin	mg/dL	17.10	$\mu\text{mol}/\text{L}$
Direct Bilirubin	mg/dL	17.10	$\mu\text{mol}/\text{L}$
Indirect Bilirubin	mg/dL	17.10	$\mu\text{mol}/\text{L}$
ALT	U/L	1	U/L
AST	U/L	1	U/L
ALP (Alkaline Phosphatase)	U/L	1	U/L

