6.5. Withdrawn/discontinuation of Subjects from Therapy

6.5.1. Reasons for Withdrawal/Early Discontinuation

A subject may discontinue or interrupt study drug for a number of reasons including, but not limited to, those listed below:

- Permanent Discontinuation
 - Death;
 - Withdrawal of consent as defined in Section 6.5.2;
 - Pregnancy
 - Lost to follow-up as defined in Section 6.5.3 (every attempt will be made by the investigator not to have subjects "lost to follow-up");
 - CrCL decrease to < 30 mL/min, confirmed by repeat testing at least 1 week later or need for kidney dialysis;
 - Investigator judgment due to:

SAE or other safety concern e.g.,

- Major life-threatening bleeding
- Onset of clinical jaundice or other overt signs of liver toxicity
- Unfavorable benefit-to-risk evaluation for continuing anticoagulant treatment
- Termination of all or part of the study by the DSMB acting in concert with the Promoter.
- Temporary Discontinuation

Temporary discontinuations of apixaban and dalteparin for 3 or more consecutive days will be recorded in the eCRF.

Potential reasons may include:

- Short-term use of prohibited concomitant medications (see Appendix 1);
- Surgical procedures;
- Any medical condition where continuing study drug may expose the subject to an increased hazard;
- New onset of elevated liver enzymes in the absence of a known cause:
 - $-ALT > 8 \times ULN$
 - AST or ALT > 5 x ULN for more than two weeks
 - ALT or AST > 3 x ULN, but not reaching the limits in the above criteria, in combination with clinical symptoms suggestive of hepatitis
 - ALT or AST > 3 x ULN with TBL > 2 x ULN
- New onset or deteriorating renal failure <30ml/h

- Platelet count $< 50 \times 10^9 / L (50,000 / mm^3)$

In patients receiving Dalteparin who experience platelet counts between 50,000 and $100,000/\text{mm}^3$, the daily dose of Dalteparin should not be discontinued but reduced until the platelet count recovers to $\geq 100,000/\text{mm}^3$. Please refer to your local product package insert for dosing reduction guidance for this patient population.

During a study drug discontinuation, a subject can be placed on antithrombotic therapy per local guidelines and the investigator's discretion.

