6.6. Withdrawal Procedures

Follow-Up of Subjects with Study Drug Discontinuation

The investigator may contact the dedicated Medical Support Line ([contact]) in case of any questions regarding how to handle a study drug discontinuation or interruption.

All randomized subjects, including those who temporarily interrupted or discontinued study drug, will be followed for a 7-month period after randomization, except when the study is truncated as noted in Section 6.5.1.

In case of premature discontinuation of treatment, study outcomes can be collected by telephone contact until 7 months after the first dose of study drug. If the subject has an onsite visit at any time after study drug discontinuation, it is expected that a clinical status will be obtained along with any laboratory assessments deemed appropriate by the Investigator.

If the subject and investigator agree that study drug can be resumed without increased hazard to the subject, study medication may be resumed at any time, regardless of the duration of study drug interruption.

Any subject who temporarily interrupts or discontinues study drug due to confirmed liver enzyme abnormalities or jaundice in the absence of a known cause, must have an evaluation to determine the cause of the event. Evaluation may include the following depending on the clinical situation:

- Abdominal ultrasound;
- Hepatitis A, B, C, and E screening (anti-HAV IgM, HbsAg, anti-HCV plus viral titer, and evaluation for Hep E), Antinuclear antibody (ANA) and anti-SmAb, Cytomegalovirus (CMV), Epstein Barr virus (EBV);
- Additional evaluations as deemed appropriate by the investigator to exclude other causes of liver enzyme and bilirubin elevations.

Follow-up of liver enzymes and bilirubin (total and direct) should be performed on a weekly basis until the values return to baseline.

All laboratory results, including local laboratory reference ranges are to be recorded in the eCRF.

All clinically significant hepatic enzyme abnormalities and/or hepatic events are to be documented in the eCRF and prompt submission of the adjudication dossier should also occur when indicated.

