9.1.2 Adverse Events of Special Interest (AESI)

In this study, the following adverse events of special interest (AESI) are to be reported to CRO/Promoter immediately, regardless of whether these reports are classified as serious or unexpected:

• potential or suspected cases of liver injury including but not limited to liver test abnormalities, jaundice, hepatitis or cholestasis.

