9.2 Collection, Reporting and Documentation of AEs

This study will follow a targeted approach to AE and SAE collection and reporting. All AEs occurring after the subject signs the ICF and through Month 6 or the global EOT date, whichever occurs first, whether observed by the Investigator or reported by the subject, will be recorded on the Adverse Events section of the eCRF if they fulfill one of the following criteria:

- 1) meet seriousness criteria;
- 2) result in interruption or discontinuation of the assigned study drug;
- 3) meet criteria as a study outcome; or
- 4) an event of special interest.

All laboratory, vital sign, or electrocardiogram (ECG) values should be evaluated by the Investigator regarding clinical significance. Isolated abnormal laboratory results or vital sign findings or ECG findings should be reported as AEs if they are symptomatic, result in study drug discontinuation, require corrective treatment, or are otherwise defined as an AE of Special Interest (AESI).

Clinically significant abnormal laboratory findings associated with the subject's cancer or other pre-existing conditions will not be reported as AEs or SAEs unless judged by the Investigator as more severe than expected for the subject's condition and meet the criteria for targeted AE and SAE reporting.

Medical conditions (including laboratory values/vital signs that are out of range) that were diagnosed or known to exist prior to informed consent will be recorded as part of medical history.

All SAEs occurring after informed consent for study participation has been obtained, which are considered not related with the subject's cancer or other pre-existing conditions,

are to be reported according to the procedures for Serious Adverse Event Reporting-Procedure for Investigators.

A preplanned (prior to signing the Informed Consent Form) procedure or treatment requiring hospitalization for pre-existing conditions which do not worsen in severity should not be reported as SAEs.

For deaths, the underlying or immediate cause of death should always be reported as an SAE. When a subject dies from disease progression of pre-existing cancer with no other immediate causes, "disease progression" should be reported as an SAE. In addition, any serious, untoward event that may occur subsequent to the reporting period that the Investigator assesses as related to study drug should also be reported and managed as an SAE.

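### SAP 10.9.2 plans no by-arm count of worst post-baseline ALT, AST or bilirubin at the protocol's own multiples of ULN, singly or jointly, and no rule for unscheduled liver samples

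*SAP*

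**What the plan says.** **Planned laboratory summaries.** SAP 10.9.2 states: "Clinical laboratory data will be summarized for each treatment group at each measurement time point and for each patient's final post-baseline measurement". Three forms follow: mean, SD, median and range at each time point; change from baseline; and "with shift tables summarizing the frequencies of patients below, within, and above the normal ranges at each time point as compared with baseline". All values are also listed, with out-of-range values flagged. Protocol 10.7 prescribes the same set.

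**Liver levels in the protocol.** Protocol 6.5.1 gives possible reasons for temporary interruption when enzymes newly rise without a known cause. They are ALT >8x ULN; "AST or ALT > 5 x ULN for more than two weeks"; ALT or AST >3x ULN with symptoms; and "ALT or AST > 3 x ULN with TBL > 2 x ULN".

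**AESI.** Protocol 9.1.2 has one entry: "potential or suspected cases of liver injury including but not limited to liver test abnormalities, jaundice, hepatitis or cholestasis". SAP 10.9.1 counts patients with an AESI in its overview of adverse events and tabulates AESIs by treatment group, System Organ Class and Preferred Term.

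**Sampling.** Liver tests are scheduled at screening, 4 weeks, 3 months and end of treatment, with unscheduled visits possible. For patients who interrupt or stop drug because of a confirmed, unexplained liver abnormality, Protocol 6.6 adds: "Follow-up of liver enzymes and bilirubin (total and direct) should be performed on a weekly basis until the values return to baseline". The same section says: "All laboratory results, including local laboratory reference ranges are to be recorded in the eCRF".

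**The concern.** The protocol expresses liver signals as multiples of ULN, and one of them as a combination of enzyme and bilirubin. The laboratory section of the SAP uses neither scale. Its top category starts at the upper limit of normal and has no ceiling, it takes each parameter separately, and its one cross-visit summary per patient is the last value, not the worst.

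At stake is whether the final report can say how many patients in each arm reached a given laboratory level, whatever the investigator thought the cause was. Without that count, the arms are compared at these levels only through reported terms. Those reports come from investigators who know the treatment, in patients whose cancer often offers another explanation.

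**Working it through.** The plan gives no figure on this point to reproduce. The check sets the sections side by side and adds two small calculations.

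**1. What each planned output shows about the 6.5.1 levels**

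| Level in Protocol 6.5.1 | Shift table | Mean, median, range, change | Final value |
|---|---|---|---|
| ALT >8x ULN | Same cell as any value above normal | Largest value at a visit; not how many patients | Last value only |
| ALT or AST >5x for over two weeks | Same cell; no duration | No duration | Last value only |
| ALT or AST >3x with bilirubin >2x | Separate tables; not linked within patient | Not linked | Not linked |

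**2. Ceiling of the shift table.** Exclusion 14 rules out ALT at 3x ULN or more and bilirubin at 2x or more, and sets no AST limit. A patient at 2.5x ULN is therefore eligible. A rise to 9x is tabulated as above-to-above. A patient going from normal to 1.1x ULN is tabulated as a shift.

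**3. How many patients this could affect.** Planned patients per arm: 1168 / 2 = 584. The documents do not give the share entering with ALT 1-3x ULN, so it is assumed to be 5-20%:
- 0.05 x 584 = 29
- 0.10 x 584 = 58
- 0.20 x 584 = 117

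These patients have no higher category to move to. The figures are not predicted numbers of liver events.

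**4. Constructed example (all data assumed).** One arm of 584 patients at one visit, ALT in multiples of ULN, lognormal with median about 0.55 and log-SD 0.5. Among patients above normal, k are set to 1.2x in one version and 9x in the other.

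| k set to 9x | Above normal | Median | Maximum | Patients >3x |
|---|---|---|---|---|
| 0 | 49 | 0.553 | 2.59 | 0 |
| 3 | 49 | 0.553 | 9.0 | 3 |
| 6 | 49 | 0.553 | 9.0 | 6 |
| 12 | 49 | 0.553 | 9.0 | 12 |

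The above-normal count and the median do not change. The maximum shows that an extreme value occurred, but is 9.0 whether 3, 6 or 12 patients had it. Only the threshold count separates the rows.

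**5. Timing.** A peak at a scheduled visit enters that visit's statistics. A peak between visits is caught only by an unscheduled or weekly sample. The SAP does not say whether such samples form a time point, are assigned to a visit or are left out. If weekly samples taken until recovery count as the final measurement, that summary shows the recovered value.

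**6. Availability of the ULN.** The planned below/within/above tables already need a reference range for each value, and Protocol 6.6 sends local ranges to the eCRF. SAP 10.9.1.1 already tabulates CK-MB, troponin and CK at 2x ULN for myocardial infarction, so the format is not new to this plan.

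**The case against.** The strongest reply is that these patients are already captured as adverse events.
- Protocol 9.2 records events of special interest and events that interrupt study drug. Section 9.2.1 requires AESI reports whether or not the event is thought drug-related.
- Section 9.3 records laboratory abnormalities that lead to omission of drug. Section 6.6 requires clinically significant hepatic enzyme abnormalities to be documented, with an adjudication dossier when indicated.
- SAP 10.9.1 then counts AESIs, and AE-related temporary interruptions, by arm.

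This stands, and it rules out some stronger readings. A reader might infer that liver injury is never compared between arms; it is, as an AESI. A reader might take 6.5.1 as the definition of the AESI; it is a list of possible reasons for interruption, while 9.1.2 is broader and has no cut-off. A reader might infer that peaks are reported as recovered values; scheduled-visit peaks enter that visit's range, change and shift summaries, and every value is listed.

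What the reply does not supply is a count at a laboratory level. The AESI table sorts by reported term. The interruption count covers all adverse events, and the breakdown of AE-related discontinuations in SAP 10.1 has no liver category. Reporting is also uneven in principle: Protocol 9.2 asks for isolated laboratory abnormalities that are AESIs, yet its next paragraph begins "Clinically significant abnormal laboratory findings associated with the subject's cancer or other pre-existing conditions will not be reported as AEs or SAEs unless", followed by a severity judgement and the targeted-reporting criteria. How the two apply to an enzyme rise put down to cancer is left to the site.

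Finally, the separate TLF Shells document named in SAP section 14 was not available, so extra tables there cannot be excluded.

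**Conclusion.** The point holds as a gap in the laboratory analysis. The SAP text specifies no by-arm count of worst post-baseline ALT, AST or bilirubin at the multiples of ULN in Protocol 6.5.1, no joint enzyme-bilirubin count, and no rule for off-schedule samples. By-arm liver counts rest on reported AESI terms and AE-related interruptions.

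The absence of the counts, the single above-normal category and the missing sample rule are read directly from the text. The 29 to 117 patients per arm depend on the assumed 5-20% baseline share, and the constructed example only illustrates the mechanism. No claim is made about how far arm means would move: that would need a ULN, a baseline level, a spread and a case count that the documents do not give.

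The documents do not support saying that a liver signal would be hidden. The range, the listing and the AESI table would each show something. They would not show how many patients per arm passed each level on a common rule. Neither the primary efficacy conclusion nor the bleeding outcome is affected. The addition is worth making because this is the trial's only AESI and the data are already collected.

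**What to change.** Keep every summary now in SAP 10.9.2, including the final value, which Protocol 10.7 also prescribes. Add, by arm, for the safety set:

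- **Worst-value shift table.** For ALT, AST and total bilirubin, take the worst value from first dose to 30 days after last dose, including unscheduled and weekly follow-up samples. Express it as a multiple of the local ULN and cross-tabulate baseline category against worst category at the cut-points already in Protocol 6.5.1: >3x, >5x and >8x for enzymes (6.5.1 applies >8x to ALT only) and >2x for bilirubin.
- **Joint count.** Number of patients with ALT or AST >3x ULN together with total bilirubin >2x ULN, regardless of attributed cause. State whether both values must come from the same sample date; the protocol does not say.
- **Denominator.** Patients with a baseline and at least one post-baseline value.
- **Label.** Call these laboratory threshold counts. They are not the AESI definition, and they omit the duration, symptom and unexplained-cause conditions in 6.5.1. They change no rule for managing patients.

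The cost is a few lines of SAP text and one or two tables, with no new samples or visits. The drawback is that worst-value figures will look less favourable in both arms, because cancer and its treatment also raise liver tests; the by-arm layout lets the reader allow for that.
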